2.5.4 Supportive analyses

NA

Subgroup analyses for the primary endpoint

The primary endpoint of PFS will be summarized for the subgroups specified in [Section 2.2.1](#) and using the same conventions as for the primary analysis.

For each of the subgroups, the following analyses will be performed using the FAS:

- Kaplan-Meier estimates of the survival distribution of PFS

Efficacy analyses in subgroups are intended to explore the consistency (homogeneity) of treatment effect. No inferential statistics (p-values) will be produced for the subgroups.

Censoring pattern of PFS

Number of patients with a PFS event and number of patients censored for the PFS analysis will be summarized. In addition, a summary of reasons for PFS censoring will be provided based on the following reasons:

- 1: Ongoing without event
- 2: Lost to follow-up
- 3: Withdraw consent
- 4: Adequate assessment no longer available
- 5: Event after ≥ 2 missing tumor assessments

The PFS censoring reasons are defined in the following way.

If the time interval between the last adequate TA date and the earliest of the following dates is smaller or equal to interval of 2 missing tumor assessments (see [Section 2.5.3](#) for definition):

1. Analysis cut-off date,
2. Date of consent withdrawal,
3. Visit date of study treatment discontinuation or end of post-treatment follow-up discontinuation due to lost to follow-up.

Then the PFS censoring reason will be:

1. 'Ongoing without event',
2. 'Withdrew consent',
3. 'Lost to follow-up',

If the time interval is larger than the interval of 2 missing tumor assessments with no event observed then the PFS censoring reason will always default to 'Adequate assessment no longer available'. If the time interval between the last adequate tumor assessment date and the PFS event date is larger than the interval of 2 missing tumor assessments then the patient will be censored and the censoring reason will be 'Event documented after two or more missing tumor assessments'.

These summaries on censoring reasons will be produced.

2.6 Analysis of the key secondary objective

There is not key secondary objective in this single arm study.

2.7 Analysis of secondary efficacy objective(s)

The other secondary efficacy objectives are to:

- Evaluate pazopanib effect on overall survival (OS)
- Evaluate pazopanib effect with respect to overall response rate (ORR) and clinical benefit rate (CBR)
- Describe the duration of response (DOR) in the subset of patients with confirmed CR / PR
- Evaluate pazopanib effect with respect to PRO assessments by EQ-5D-5L and FKSI-DRS questionnaires.

2.7.1 Secondary endpoints

Overall Survival (OS)

Overall Survival (OS) is defined as the time from date of start of treatment to date of death due to any cause. A cut-off date will be established for each analysis of OS. All deaths occurring on or before the cut-off date in the FAS will be used in the OS analysis.

If a patient is not known to have died at the time of analysis cut-off, OS will be censored at the date of last contact.

The OS analyses will also be provided by the line of therapy subgroups defined in [Section 2.2.1](#).

Overall Response Rate (ORR)

ORR is defined as the proportion of patients with best overall response (BOR) of complete response (CR) or partial response (PR) according to RECIST 1.1 (see [Appendix 2](#) of the study protocol). ORR will be calculated based on the FAS using local investigators review of tumor assessment data. Tumor assessments performed before the start of any further antineoplastic therapy (i.e. any additional secondary antineoplastic therapy or surgery) will be considered in

the assessment of BOR. Palliative radiotherapy is not allowed as per protocol and those will be considered as anti-neoplastic therapy usage.

The ORR analyses will also be provided by the line of therapy subgroups defined in [Section 2.2.1](#).

Clinical benefit rate (CBR)

CBR is defined as the proportion of patients with a best overall response (BOR) of confirmed CR or PR, or SD or Non-CR/Non-PD lasting 24 weeks or longer, according to RECIST v1.1 criteria. A patient will be considered to have SD for 24 weeks or longer if a SD response is recorded at (24 -1) weeks or later from start of study treatment, allowing for the ± 1 week visit window for tumor assessments. CBR will be calculated using the FAS based on the investigators' tumor assessments.

Duration of response (DOR)

DOR only applies to patients whose best overall response is complete response (CR) or partial response (PR) according to RECIST v1.1 based on local investigators review of tumor assessment data. The start date is the date of first documented response of CR or PR (i.e., the start date of response, not the date when response was confirmed), and the end date is defined as the date of the first documented progression or death due to underlying cancer. Patients continuing without progression or death due to underlying cancer will be censored at the date of their last adequate tumor assessment using the censoring rule described for PFS analysis.

Time to response

Time to response (CR or PR) is the time from date of start of treatment to first documented response of CR or PR (which must be confirmed subsequently) using local investigators review of tumor assessment data and according to RECIST v1.1. All patients in the FAS will be included in the time to response calculation. Patients who did not achieve a confirmed PR or CR will be censored at:

- the maximum follow-up time (i.e. FPFV - LPLV used for the analysis) for patients who had a PFS event (i.e. either progressed or died due to any cause);
- the last adequate tumor assessment date for all other patients.

Waterfall plot to depict anti-tumor activity

Waterfall graphs will be used to depict the anti-tumor activity using FAS. These plots will display the best percentage change from baseline in the sum of diameters of all target lesions for each patient. Only patients with measurable disease at baseline will be included in the waterfall graphs. Special consideration is needed for assessments where the target lesion response is CR, PR or SD, but the appearance of a new lesion or a worsening of non-target lesions results in an overall lesion response of PD. As a conservative approach, such assessments will not be considered for display as bars in the graph, since the percentage change in the sum of diameters of target lesions reflects the non-PD target lesion response, but the overall lesion response is PD. A patient with only such assessments will be represented by a special symbol (e.g. *) in the waterfall graph. Assessments with "unknown" target lesion

response and assessments with unknown overall response will be excluded from the waterfall plots. Patients without any valid assessments will be completely excluded from the graphs.

- The total number of patients displayed in the graph will be shown and this number will be used as the denominator for calculating the percentages of patients with tumor shrinkage and tumor growth. Footnote will explain the reason for excluding some patients (due to absence of any valid assessment).
- All possible assessment scenarios are described in [Table 2-5](#).

Table 2-5 Inclusion/exclusion of assessments used in waterfall graph

	Criteria for inclusion/exclusion			Possible sources of contradictions	
case	Target response	Overall lesion response	Include in waterfall?	Non-target response	New lesion?
1	CR/PR/SD	PD	Yes but as “ only	PD	any
2	CR/PR/SD	PD	Yes but as “ only	any	Yes
3	UNK	UNK or PD	No	any	any
4	CR/PR/SD	UNK	No	UNK	No
5	CR/PR/SD	CR/PR/SD	Yes as a bar	SD/IR	No
6	PD	PD	Yes as a bar	any	any

Patient-reported outcomes (PRO)

Statistical analyses are described in [Section 2.9](#).

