Chest x-rays and ultrasound should not be used to measure tumor lesions.

Post-baseline imaging assessments

Imaging assessments as described in [Table 7-3](#) should be performed at the time points specified using the same imaging modality used at screening. Imaging assessments for response evaluation will be performed every 8 weeks (\pm 7 days) during the first year, and every 12 weeks (\pm 7 days) thereafter until study treatment discontinuation for disease progression, death, lost to follow-up, withdrawal of consent or the end of the study. Imaging assessments should be scheduled using the treatment start date (Cycle 1 Day 1) as the reference date (not the previous tumor assessment date), and should be respected regardless of whether the study treatment is temporarily withheld or unscheduled assessments performed.

Additional imaging assessments may be performed at any time during the study at the investigator's discretion to support the efficacy evaluations for a subject, as necessary. Clinical suspicion of disease progression at any time requires a physician examination and imaging assessments to be performed promptly rather than waiting for the next scheduled imaging assessment.

Each lesion that is measured at screening must be measured by the same method and when possible, the same local radiologist/physician throughout the study so that the comparison is consistent. If an off-schedule imaging assessment is performed because progression is suspected, subsequent imaging assessments should be performed in accordance with the original imaging schedule.

Partial Response (PR) and Complete Response (CR) must be confirmed by repeat assessments performed not less than 4 weeks and after the criteria for response are first met. Positron Emission Tomography (PET)/CT may be used only if the CT component is of similar diagnostic quality as a CT performed without PET, including the utilization of oral and i.v. contrast media. At the discretion of the Investigators, FDG-PET scans may be performed to document progressive disease per RECIST 1.1 ([Appendix 2](#)). If possible, a single radiologist should perform all tumor response evaluations for an individual patient. Any lesions in previously irradiated areas should not be considered measurable unless they have experienced progression since the radiotherapy. Any pre-existing radiographic findings which may mimic metastatic disease and any prior radiotherapy should be recorded in the eCRF.

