10.5.2 Other secondary efficacy objectives

Overall response rate (ORR)

ORR is defined as the proportion of patients with best overall response (BOR) of CR or PR based on local investigator's assessment according to RECIST 1.1 (see [Appendix 2](#) for details). Determination of BOR of PR or CR will be based on confirmed PR/CR as per RECIST 1.1.

ORR will be calculated based on the FAS and its exact 95% confidence interval ([Clopper and Pearson 1934](#)) will be presented.

Clinical benefit rate (CBR)

CBR is defined as the proportion of patients with a best overall response of confirmed CR, or PR or an overall lesion response of SD or Non-CR/Non-PD lasting ≥ 24 weeks based on local investigator's assessment according to RECIST 1.1.

CBR and its exact 95% confidence interval will be provided using FAS population.

Overall survival (OS)

OS is defined as the time from date of start of pazopanib treatment to date of death due to any cause. If a patient is not known to have died, then OS will be censored at the latest date the patient was known to be alive (on or before the cut-off date).

OS will be analyzed in the FAS population. The OS distribution will be estimated using the Kaplan-Meier method. The Kaplan-Meier curve will be graphically presented, and the median, 25th and 75th percentiles will be shown along with the corresponding 95% confidence intervals. OS probability at selected time-points (e.g., 6, 12 and 24 months) will also be estimated.

Duration of response (DOR)

DOR only applies to patients, whose best overall response is confirmed CR or PR, as per local investigator's assessment, according to RECIST 1.1. DOR is defined as the time from the date of first documented response of CR or PR (i.e., the start date of response, not the date when response was confirmed), to the date of the first documented progression or death due to underlying cancer, whichever comes first. In patients continuing without progression or death due to underlying cancer DOR will be censored at the date of their last adequate tumor assessment. DOR will be estimated using the Kaplan-Meier method. The median, 25th and 75th percentiles, and the corresponding 95% confidence intervals will be provided.

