- PR = at least two determinations of PR or better at least 4 weeks apart before progression (and not qualifying for a CR) where confirmation required or one determination of PR prior to progression where confirmation not required
- SD = at least one SD assessment (or better) > 6 weeks start of treatment (and not qualifying for CR or PR).
- PD = progression ≤ 12 weeks after start of treatment (and not qualifying for CR, PR or SD).
- UNK = all other cases (i.e. not qualifying for confirmed CR or PR and without SD after more than 6 weeks or early progression within the first 12 weeks)

The time durations specified in the SD/PD/UNK definitions above are defaults based on a 6 week tumor assessment frequency. However these may be modified for specific indications which are more or less aggressive. In addition, it is envisaged that the time duration may also take into account assessment windows. E.g., if the assessment occurs every 6 weeks with a time window of \pm 7 days, a BOR of SD would require a SD or better response longer than 5 weeks after randomization/start of treatment.

Overall lesion responses of CR must stay the same until progression sets in, with the exception of a UNK status. A patient who had a CR cannot subsequently have a lower status other than a PD, e.g., PR or SD, as this would imply a progression based on one or more lesions reappearing, in which case the status would become a PD.

Once an overall lesion response of PR is observed (which may have to be a confirmed PR depending on the study) this assignment must stay the same or improve over time until progression sets in, with the exception of an UNK status. However, in studies where confirmation of response is required, if a patient has a single PR ($\geq 30\%$ reduction of tumor burden compared to baseline) at one assessment, followed by a $< 30\%$ reduction from baseline at the next assessment (but not $\geq 20\%$ increase from previous smallest sum), the objective status at that assessment should be SD. Once a confirmed PR was seen, the overall lesion response should be considered PR (or UNK) until progression is documented or the lesions totally

disappear in which case a CR assignment is applicable. In studies where confirmation of response is not required after a single PR the overall lesion response should still be considered PR (or UNK) until progression is documented or the lesion totally disappears in which case a CR assignment is applicable.

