Duration of overall complete response (CR): For patients with a CR (which may have to be confirmed) the start date is the date of first documented CR and the end date and censoring is defined the same as that for time to progression.

Duration of stable disease (CR/PR/SD): For patients with a CR or PR (which may have to be confirmed) or SD the start and end date as well as censoring is defined the same as that for time to progression.

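### The SAP's 24-week test for stable disease in CBR omits responses better than SD, so on a literal reading some patients with a first response at week 24 are not counted while plain SD is

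*SAP*

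**What the plan says.** SAP 2.7.1 defines CBR as the proportion of patients with a "best overall response (BOR) of confirmed CR or PR, or SD or Non-CR/Non-PD lasting 24 weeks or longer". It then gives its only operational test of duration: SD has lasted 24 weeks "if a SD response is recorded at (24 -1) weeks or later from start of study treatment". The one-week allowance reflects the scan window.

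Protocol 10.5.2 has the same components, with "an overall lesion response of SD or Non-CR/Non-PD lasting" at least 24 weeks, but does not say how lasting is to be determined.

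Protocol Appendix 2, section 3.1, supplies the best overall response (BOR) rules. For a confirmed partial response, "PR = at least two determinations of PR or better at least 4 weeks apart before progression". For stable disease, "SD = at least one SD assessment (or better) > 6 weeks start of treatment". Where a single PR is followed by a reduction below 30% without progression, "the objective status at that assessment should be SD". Protocol 7.2.1 requires confirmation: responses "must be confirmed by repeat assessments performed not less than 4 weeks and after the criteria for response are first met".

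Neither document states how CBR treats a response first seen at week 24 and never confirmed.

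**The concern.** Under Appendix 2 an unconfirmed response falls back to a BOR of SD. The patient then enters CBR only through the 24-week SD route, and the SAP tests that route by looking for a record labelled SD at week 23 or later. If the only qualifying scan was labelled PR or CR, the test finds nothing.

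Two patients with the same scan dates and the same progression date can therefore be classified differently, and the one with more tumour shrinkage is the one not counted. At stake are the correctness of a secondary endpoint and its reproducibility, since two programmers could code the sentence differently and both defend the choice.

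**Working it through.** The plan gives no expected CBR and no sample-size figure for it, so there is no planned number to reproduce beyond the threshold: 24 − 1 = 23 weeks, or 23 × 7 = 161 days after the start of treatment.

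**Inputs**
- Scans every 8 weeks (± 7 days) in the first year, hence nominal weeks 8, 16, 24, 32 and 40 (Protocol 7.2.1).
- Confirmation at least 4 weeks after the first response (Protocol 7.2.1; Appendix 2, 3.1).
- 28-day cycles (Protocol 6.1.1); primary cut-off after all patients complete 6 cycles or discontinue (SAP 2.1).
- About 100 patients (SAP 3.1); exact Clopper-Pearson intervals (SAP 2.7.2).

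**Step 1: apply both readings to scan sequences**

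| Wk 8 | Wk 16 | Wk 24 | Wk 32 | BOR | Literal SAP rule | SD or better |
|---|---|---|---|---|---|---|
| SD | SD | SD | PD | SD | counted | counted |
| SD | SD | PR | PD | SD | **not counted** | counted |
| SD | SD | PR | UNK, then none | SD | **not counted** | counted |
| SD | SD | PR | no eligible scan | SD | **not counted** | counted |
| SD | SD | PR | SD | SD | counted | counted |
| SD | SD | PR | PR | PR | counted | counted |
| SD | SD | SD | PR, then none | SD | counted | counted |

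Rows 1 and 2 show the inversion. A first CR at week 24 behaves as PR does here.

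I took all sequences of SD, PR, PD, UNK or end of scanning over weeks 8 to 40. Of 485 distinct sequences, the two readings differ in 36. Only two of the 36 contain no UNK, namely rows 2 and 4. These are counts of patterns, not of patients.

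**Step 2: how row 4 arises**
- *Primary cut-off.* 6 × 28 = 168 days = 24 weeks, and the next scheduled scan is at week 32. A late enrollee with a first PR at week 24 may have no confirming scan before the cut-off. A patient with plain SD on the same dates already counts.
- *Treatment stopped.* SAP 2.7.1 uses only assessments before further antineoplastic therapy for BOR. Appendix 2, 3.1 by default drops assessments more than 30 days after the last dose. If dosing ends at week 24, the nominal week-32 scan falls 56 days later and is ineligible under that default.

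**Step 3: size**

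One patient is 1/100 = 1 percentage point. The base rate and the number affected below are assumptions. Limits are the Beta(k, n − k + 1) 2.5% and Beta(k + 1, n − k) 97.5% quantiles with n = 100.

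| Base CBR | As is | +1 patient | +3 | +5 |
|---|---|---|---|---|
| 30% | 21.2–40.0 | 31%: 22.1–41.0 | 33%: 23.9–43.1 | 35%: 25.7–45.2 |
| 40% | 30.3–50.3 | 41%: 31.3–51.3 | 43%: 33.1–53.3 | 45%: 35.0–55.3 |
| 50% | 39.8–60.2 | 51%: 40.8–61.1 | 53%: 42.8–63.1 | 55%: 44.7–65.0 |

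The shift is small beside an interval about 20 points wide.

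**The case against.** The best reply is that the SAP sentence gives a sufficient condition, not a necessary one. It sits inside a definition that follows RECIST 1.1, and Appendix 2 gives this patient a BOR of SD. Appendix 2, 3.2.6 also defines a duration of stable disease that takes the three categories together: "For patients with a CR or PR (which may have to be confirmed) or SD the start and end date" are those of time to progression. A sensible programmer could credit the patient. This stands in part: a failure count is possible rather than certain. But that variable is offered as an optional extra for large Phase III studies, and the SAP sentence is the only operational rule for CBR.

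Several stronger readings are tempting, and the documents do not support them:

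- *Every unconfirmed PR at week 24 fails.* It does not. A later SD meets the rule, a later PR confirms the response, and a PR at week 8 or 16 is itself confirmed by one at week 24. A first PR at week 32 normally follows a qualifying SD at week 24.
- *Non-CR/Non-PD is left without a rule.* Appendix 2, 3.2.9 treats it in general as equivalent to SD for endpoints. It arises only in patients with non-target disease alone, and inclusion criterion 4 requires measurable disease.
- *Appendix 2 already prescribes SD or better for the 24-week test.* Its SD-or-better wording is a BOR rule at 6 weeks. Its own CBR definition in 3.1 also lacks those words.

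The cut-off case is also limited. Only patients enrolled near the end can be awaiting confirmation, and the final analysis, two years after the last patient starts, should settle most of these. ORR likewise leaves a pending response uncounted, but there plain SD is uncounted too, so no inversion results.

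**Conclusion.** The point holds in a narrow form. Read literally, the SAP test leaves out of CBR a patient whose first PR or CR is at week 24 and is followed by PD, UNK or no further eligible scan, while counting a patient with plain SD and the same progression time. With complete, evaluable scans to week 24, this is the only affected group; a missing or UNK scan at week 24 can extend it to a first response at week 32.

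The effect is about 1 percentage point of CBR per affected patient at about 100 patients. A reader might infer an undercount of a few points, but the documents give neither an expected CBR nor the frequency of late first responses, so no total can be derived. CBR is a descriptive secondary endpoint with no hypothesis test; PFS, OS and ORR do not depend on this rule. It is a minor correction, worth making because the rule as worded orders outcomes the wrong way.

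**What to change.** Reword the duration test in SAP 2.7.1 along these lines: *stable disease counts as lasting 24 weeks when an overall lesion response of SD or better (Non-CR/Non-PD being treated as SD, per Appendix 2) is recorded at (24 − 1) weeks or later after treatment start, with no earlier PD.* Use the same eligible assessments as for BOR. An unconfirmed response then enters CBR as stable disease, and ORR does not change.

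The cost is a few words in the SAP and a small change to the derivation code, with no new data. It should be made before database lock.

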2.5.3 Handling of missing values/censoring/discontinuations

In the primary analysis, PFS will be censored at the date of the last adequate tumor assessment if no PFS event (disease progression or death due to any cause) is observed prior to the analysis cut-off date.

PFS events documented after the initiation of new anti-neoplastic therapy (i.e. RECIST v1.1 documented disease progression or death) will be considered for the primary analysis provided tumor assessments continue after initiation of new cancer therapy.

The date of last adequate tumor assessment is the date of the last tumor assessment with overall lesion response of CR, PR or SD before an event or a censoring reason occurred. In this case the last tumor evaluation date at that assessment will be used. If no post-baseline assessments are available (before an event or a censoring reason occurred) then the date of start date of treatment will be used.

In particular, PFS will be censored at the last adequate tumor assessment if one of the following occurs: absence of event; the event occurred after two or more missing tumor assessments. The term "missing adequate tumor assessment" is defined as a tumor assessment (TA) not performed or tumor assessment with overall lesion response of "UNK". The rule to determine number of missing TAs is based on the time interval between the date of last adequate tumor assessment and the date of an event. If the interval is greater than twice the protocol-specified interval between the TAs and 2 times the protocol-allowed time window around assessments, then the number of missing assessments will be 2 or more.

Refer to [Table 2-4](#) for censoring and event date options and outcomes for PFS.

Table 2-4 Outcome and event/censor dates for PFS analysis

Situation	Date	Outcome
No baseline assessment	Date of start of study treatment	Censored
Progression or death at or before next scheduled Assessment	Date of progression (or death)	Progressed

Situation	Date	Outcome
Progression or death after exactly one missing assessment	Date of progression (or death)	Progressed
Progression or death after two or more missing assessments	Date of last adequate assessment prior to missed assessment	Censored
No progression (or death)	Date of last adequate assessment	Censored
Treatment discontinuation due to 'Disease progression' without documented progression, i.e. clinical progression based on investigator claim	Date of last adequate assessment	Censored

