2.7.3 Handling of missing values/censoring/discontinuations

Overall Survival

If a patient is not known to have died at the time of analysis cut-off, then OS will be censored at the date of last known date patient was alive, i.e., last contact date (see [Section 2.1.1](#)).

ORR (same for CBR)

Patients with unknown or missing best overall response (BOR) will be counted as failures. If there is no baseline tumor assessment, all post-baseline overall lesion responses are expected to be ‘Unknown’. If no valid post-baseline tumor assessments are available, the best overall response must be “Unknown” unless progression is reported. For the computation of ORR, these patients will be included in the FAS and will be counted as ‘failures’.

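### As written, the SAP's waterfall percentages can overstate tumour shrinkage on pazopanib relative to the SAP's own FAS and best-overall-response rules

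*SAP*

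**What the plan says.** SAP 2.7.1 presents the waterfall plot as an FAS display limited to patients with measurable disease at baseline. The measure is the best change: "These plots will display the best percentage change from baseline in the sum of diameters of all target lesions for each patient". No time limit other than the data cut-off applies.

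Display rules, from the text and Table 2-5:

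- Cases 1 and 2 (target CR/PR/SD, overall PD): no bar. "A patient with only such assessments will be represented by a special symbol".
- Case 3 (target UNK, overall UNK or PD): assessment not included.
- Case 4 (target CR/PR/SD, overall UNK): not included; "assessments with unknown overall response will be excluded from the waterfall plots".
- Cases 5 and 6 (target and overall response agree): drawn as a bar.
- "Patients without any valid assessments will be completely excluded from the graphs".

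The number displayed is shown, a footnote explains exclusions, and "this number will be used as the denominator for calculating the percentages of patients with tumor shrinkage and tumor growth".

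Two neighbouring rules differ. For BOR, the eligible scans are "Tumor assessments performed before the start of any further antineoplastic therapy" (SAP 2.7.1). For ORR, "Patients with unknown or missing best overall response (BOR) will be counted as failures", and those patients stay in the FAS (SAP 2.7.3).

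**The concern.** The shrinkage percentage and ORR will describe tumour activity in the same report, yet they use different patients and possibly different scans. The SAP gives no reason for the difference.

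The scan set matters because a best change can only stay the same or improve as scans are added. If scans made after the start of another therapy enter the data, a reduction produced by that therapy can be drawn as pazopanib activity. The patient set matters because a documented progressor can drop out of both numerator and denominator for no reason other than an unmeasured target lesion.

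The trial has a single arm, and Protocol 2.2 says its results will be judged against previously reported data. A shrinkage percentage may therefore be quoted on its own.

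**Working it through.** The documents state no expected shrinkage percentage and no expected number of undisplayed patients, so there is no plan figure to reproduce. The check is a reading of the rules, followed by arithmetic on labelled assumptions.

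**Step 1. Can scans on a later therapy enter the plot?**

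- SAP 2.1 uses all data up to the cut-off unless a section says otherwise. The waterfall text says nothing on new therapy.
- Protocol 7.1.3 continues scans every 8 weeks in patients who stop without progression. Starting another therapy is not among the reasons to stop scanning.
- SAP 2.5.3 anticipates such scans for PFS: events after new therapy "will be considered for the primary analysis provided tumor assessments continue after initiation of new cancer therapy". Table 2-4 ignores new therapy when assigning PFS dates.
- Protocol Appendix 2, section 3.1, ordinarily excludes scans after alternative therapy, but for BOR only.
- Protocol 6.3.3 says patients should not receive other anti-cancer therapy before established recurrence.

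So such scans can exist and nothing keeps them out of the plot, but they should be few.

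**Step 2. Can a documented progressor vanish?**

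Appendix 2 Table 2-3 assigns overall PD to any new lesion, whatever the target response. Appendix 2 Table 2-1 gives target UNK when a target is unassessed or assessed by another method. The two together are case 3. If all of a patient's post-baseline scans are of this type (or otherwise invalid), the patient is not displayed. The same progressor with all targets measured and in the CR/PR/SD range is shown as a symbol and, on the natural reading of the number displayed, stays in the denominator.

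**Step 3. Denominator.**

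Let N be FAS patients with measurable disease, D those displayed, S displayed patients with shrinkage, e undisplayed patients whose targets in fact shrank, and m = (N - D)/N.

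- Displayed percentage = S/D.
- FAS percentage = (S + e)/N.
- If e = 0, the ratio of the first to the second is N/D = 1/(1 - m).

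Take N = 100 (planned enrolment; inclusion criterion 4 requires measurable disease). Assume displayed shrinkage of 60% and e = 0:

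| Not displayed | Displayed | FAS | Gap (points) | 1/(1 - m) |
|---|---|---|---|---|
| 5 | 57/95 = 60.0% | 57.0% | 3.0 | 1.053 |
| 10 | 54/90 = 60.0% | 54.0% | 6.0 | 1.111 |
| 15 | 51/85 = 60.0% | 51.0% | 9.0 | 1.176 |
| 20 | 48/80 = 60.0% | 48.0% | 12.0 | 1.250 |

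With displayed shrinkage of about 50% to 70%, the gap runs from 2.5 points (48/95 = 50.5% against 48%) to 14 points (56/80 = 70% against 56%).

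**Step 4. Later-therapy scans added to the 54/90 example.** If 2 further displayed patients reach shrinkage only on a later therapy, the figure is 56/90 = 62.2%; with 5 it is 59/90 = 65.6%. The FAS figure with a cut at new therapy stays at 54.0%.

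**Step 5. Rules that push the other way, same example.**

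- Case 4 can remove patients whose targets shrank. If e = 6, the FAS figure is 60/100 = 60.0% and there is no gap. If e = 8, it is 62.0% and the displayed 60.0% is too low.
- Cases 1 and 2 draw no bar even where targets shrank. If 3 or 6 symbol patients had target shrinkage, counting them would give 57/90 = 63.3% or 60/90 = 66.7%.

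**The case against.** The strongest reply is that a reader might infer that shrinkage is overstated and that the error runs one way. The documents do not support that.

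- Cases 1, 2 and 4 can lower the figure, as Step 5 shows.
- It is tempting to say that the undisplayed patients are mostly those doing worst. Early deaths would be among them, but Appendix 2 sections 2.2 and 2.4.2 also produce UNK from a change in contrast use or imaging method, which says nothing about prognosis. No proportions are given.
- It is tempting to say that the SAP admits scans on the next therapy. It is silent. The passage in SAP 2.5.3 governs PFS events only, and Protocol 6.3.3 limits how many such scans there can be.
- Case 3 removes an assessment, not a patient. The patient is lost only when no other scan is valid.
- Scoring every unmeasured patient as not showing shrinkage is itself a debatable choice for a descriptive plot.
- The displayed number and a footnote are promised, ORR is already computed on the FAS, and the plot is not an endpoint in SAP Table 1-1.

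Most of this stands and limits the point to what can happen. Three things remain. The silence on new therapy, combined with the all-data default, leaves a real ambiguity that the BOR rule in the same section avoids. The footnote would attribute a case 3 exclusion to lack of a valid assessment although progression was documented. Disclosing the displayed number does not give the FAS-based percentage or the reasons for exclusion.

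**Conclusion.** The point holds as a possibility, measured against the SAP's own conventions: the waterfall percentages can overstate shrinkage on pazopanib because later-therapy scans are not cut, case 3 progressors can drop out, and the denominator is displayed patients only.

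The size cannot be taken from the documents. The factor 1/(1 - m) requires that no undisplayed patient shrank. The gaps of 2.5 to 14 points rest on that condition and on assumed values of 5 to 20 undisplayed patients in 100 and about 50% to 70% displayed shrinkage. They compare two denominators and should not be read as estimates of bias. A reader might take them as proof of inflation, but Step 5 shows that plausible counts under cases 1, 2 and 4 can cancel or reverse the gap.

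The growth percentage shares the denominator. The primary PFS analysis and ORR are unaffected. This is a cheap improvement to a descriptive display.

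**What to change.** Make three wording changes in SAP 2.7.1 and Table 2-5:

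1. Restrict the best percentage change to scans eligible for BOR, that is, before any further antineoplastic therapy as that section defines it.
2. Split case 3. Patients whose only usable information is overall PD with target UNK get the same symbol as cases 1 and 2 and count in the denominator. Assessments with both responses UNK stay excluded.
3. Report the shrinkage and growth percentages on FAS patients with measurable disease beside the displayed-patient percentages. Count the excluded patients by reason (for example, no post-baseline scan, or unknown target or overall response), so that a reader can see how far the result depends on treating them as not showing shrinkage.

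No new data are needed. The cost is a slightly less favourable headline percentage and a little more programming and reporting.
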